3.1 APPROPRIATENESS OF MEASUREMENTS

The efficacy and safety assessments used in this study are standard for the evaluation of therapy in patients with COPD.

4 STUDY DESIGN

4.1 OVERALL DESIGN

Multinational, randomized, double-blind, placebo controlled, parallel group (2 groups), Proof of Concept (PoC) study that is designed to assess the efficacy, safety, and tolerability of SAR440340 in patients with moderate-to-severe COPD on an established LABA, LAMA and/or ICS background therapy (double or triple therapy). Patients will be treated with SAR440340 or placebo for a minimum of 24 weeks and up to a maximum of 52 weeks*, and a 20-week safety follow-up period.

**This study employs a variable treatment duration from 24 to 52 weeks to maximize data for the primary endpoint (annualized rate of exacerbation) in a time-efficient manner. Patients enrolled in the trial will remain in the treatment period for up to a maximum of 52 weeks or until the last patient randomized completes a minimum treatment period of 24 weeks. Of note, the accrual and drop-out rates will be closely monitored. If the accrual rates are significantly lower than planned and/or the drop-out rates are higher than expected, the minimum treatment duration may be extended to achieve the desired amount of total exposure. The maximum treatment duration of 52 weeks will not be changed.*

The study duration is outlined below:

- Screening period (10 days to 4 weeks)
- Randomized IMP treatment period (24 to 52 weeks)
- Post IMP safety follow-up treatment period (20 weeks).

The randomization/baseline Visit is defined as Day 1. The visit schedule should be adhered to within ± 3 days for the screening period and randomized IMP treatment period, and ± 5 days for the 2 visits during the post IMP treatment period.

At screening, patients must be on Standard of Care background therapy, for 3 months prior to Visit 2/Randomization and at a stable dose for at least 1 month prior to the Screening Visit 1, including either:

- Double therapy: LABA + LAMA or ICS + LABA or ICS + LAMA.
- OR
- Triple therapy: ICS + LABA + LAMA.

Patients who satisfy the inclusion and exclusion criteria will be randomized (1:1) to:

- SAR440340 (300 mg) administered as 2 SC injections every 2 weeks (q2w) for 24 to 52 weeks
- Matching placebo for SAR440340 administered as 2 SC injections q2w for 24 to 52 weeks

It is planned to enroll approximately 50% of patients on ICS-containing background therapy (ICS + LABA; ICS + LAMA or ICS + LABA + LAMA).

Patients must be willing to stay on their established background medication for COPD throughout the duration of the study.

Treatment discontinuation follow-up:

Patients who withdraw from study treatment (prior to completing the planned duration of IMP treatment) will perform, as soon as possible, the early treatment discontinuation visit (ETD) with all assessments normally planned for the EOT visit, to assure a complete clinical assessment in close temporal proximity to the premature termination of study treatment is available. In addition, and to allow assessment of patient outcomes over the stipulated study period, patients will be asked and encouraged to complete all remaining study treatment visits, and participate in all safety follow-up assessments according to the visit schedule with a +/-5 day window. For such patients the assessment schedule will be reduced (See study flowchart for patients after permanent treatment discontinuation in [Section 1.3.2](#)) and alternate visits during the planned treatment period may be conducted by phone (those with odd visit numbers, except for the planned EOT), as can visits F1 and F2.

Under exceptional circumstances when a patient cannot come to the site for a scheduled visit, a phone contact can be made. During the phone contact, at least information about AEs, concomitant medication and COPD exacerbation events should be collected.

Post IMP treatment follow-up:

Upon completing the 24-52 weeks randomized IMP treatment, patients will continue their established ICS/LABA/LAMA therapy and enter the 20-week safety follow-up period.

4.2 SCIENTIFIC RATIONALE FOR STUDY DESIGN

The first-in-human study (R3500-HV-1551) to investigate safety and pharmacokinetics (PK) of a single intravenous (IV) infusion of 0.3, 1, 3 or 10 mg/kg or a single subcutaneous (SC) injection of 150 mg of SAR440340 in normal healthy volunteers was completed. Treatment with SAR440340 was generally well-tolerated. No deaths and no serious adverse events (SAEs) were reported.

The first-in-patient study (R3500-AS-1619) to investigate safety, tolerability, PK, and pharmacodynamic (PD) effects of a repeated SC administration of SAR440340 at 2 dose levels (75 and 150 mg), every week for 4 weeks, in adult patients with moderate asthma is ongoing, with all patients in the postdosing follow-up period. Unblinded safety data (as of February 23, 2018) have demonstrated that SAR440340 is so far well tolerated. No SAE's or deaths have been reported.

A PD study (R3500-AS-1633) to assess the effects of a single IV dose of 10 mg/kg SAR440340, 2 repeated SC doses of dupilumab (600 mg loading dose then 300 mg dose), and the coadministration of SAR440340 with dupilumab on markers of inflammation after Bronchial

Allergen Challenge in patients with mild allergic asthma is ongoing. At the time of writing this protocol, acceptable safety and tolerability was observed from the blinded assessments in this study.

A randomized, placebo-controlled study design where the effects of the IMP is assessed on top of optimized background therapy is considered to be the most appropriate design to explore the efficacy and safety of a novel biologic therapy in COPD. Similar study designs and endpoints have been employed for recent studies with other biologics and are considered “state-of-the-art” for studies in COPD (7, 8). The selection of the dose of IMP and duration of study treatment are explained in [Section 4.3](#) and [Section 9.2](#), respectively.

4.3 JUSTIFICATION FOR DOSE

The dose regimen of SAR440340 selected for this study is 300 mg SC administered every 2 weeks (q2w). This dosage regimen is predicted to achieve single-dose exposure which falls well within the maximum exposure achieved by the single 10 mg/kg IV dose shown to be safe in the FIH (R3500-HV-1551) single-ascending dose study. Safety after repeated dose administration of SAR440340 can be inferred from the results of the chronic safety study in cynomolgus monkeys where doses as high as 100 mg/kg were administered weekly SC for 26 weeks. Based on systemic drug exposures (area under the concentration [AUC]-time curves) in the toxicology studies, the proposed SC dose of 300 mg q2w provides a safety margin (exposure multiple based on predicted human exposure) of 13.7-29.8 for a proposed 24-52 week study.

In addition to safety, PK-PD factors were considered. Based on modeling and simulation of SAR440340 HV-1551 FIH drug concentration, the 300 mg q2w regimen is expected to achieve a minimum concentration at steady state which is approximately 5-fold higher than the concentration of SAR440340 (17 mg/L) that showed efficacy consistently across all endpoints in an HDM-induced chronic lung inflammation mouse model. The higher-fold exposure of the 300 mg q2w regimen should conservatively ensure all patients are above this efficacy threshold when taking into account PK inter-individual variability, as well as the uncertainty in translating the PD of SAR440340 from the HDM mouse model to COPD in humans.

4.4 END OF STUDY DEFINITION

A participant is considered to have completed the study if he/she has completed all phases of the study including the end of study visit. This study has a variable treatment period, therefore all participants who complete the planned treatment period of 24 to 52 weeks and all phases for the follow-up including the end of study visit are completers.

The end of this study is defined as completion of the last patient last visit which will occur at the end of a 20-week safety follow-up period for the final patient(s) who complete(s) the study as per protocol.

For patients who discontinue the planned treatment, the recommended follow-up is described in [Section 4.1](#).

5 STUDY POPULATION

Prospective approval of protocol deviations to recruitment and enrollment criteria, also known as protocol waivers or exemptions, is not permitted.

5.1 INCLUSION CRITERIA

Participants are eligible to be included in the study only if all of the following criteria apply:

Age

Participant must be 40 to 75 years of age inclusive, at the time of signing the informed consent.

Type of participant and disease characteristics

- I 01. Participants with a diagnosis of COPD for at least 1 year (based on Global Initiative for Chronic Obstructive Lung Disease [GOLD] definition, see (1)).
- I 02. Participants with moderate-to-severe COPD (post-bronchodilator FEV1/forced vital capacity [FVC] <70% and post-bronchodilator FEV1 % predicted <80%, but \geq 30%) at Visits 1 and 2.
- I 03. Participants with COPD Assessment Test (CAT) score \geq 10 at Screening Visit 1 and Visit 2/Randomization.
- I 04. Participants with reported history of signs and symptoms of chronic bronchitis (chronic productive cough for 3 months in the year up to screening in a patient in whom other causes of chronic cough [eg, gastroesophageal reflux, chronic rhinosinusitis, bronchiectasis] have been excluded).
- I 05. Participants with a documented history (eg, medical record verification) of \geq 2 moderate exacerbations or \geq 1 severe exacerbation within the year prior to screening
 - a moderate exacerbation is defined as an AECOPD requiring systemic corticosteroids (oral, intravenous, or intramuscular) and/or treatment with antibiotics (however, use of antibiotics alone does not qualify as a "moderate exacerbation" unless documentation is available that use of antibiotics was necessary for treatment of worsening symptoms of COPD)
 - a severe exacerbation is defined as an AECOPD that required a hospitalization.
- I 06. Participants with Standard of Care background therapy, for 3 months prior to Visit 2/Randomization and at a stable dose for at least 1 month prior to the screening, including either:
 - Double therapy: LABA + LAMA or ICS + LABA or ICS + LAMA.

OR

Triple therapy: ICS + LABA + LAMA.

I 07. Current or former smokers with a smoking history of ≥ 10 packs-year.

Weight

I 08. Body mass index (BMI) ≥ 18.0 kg/m² (inclusive).

Sex

I 09. Male or Female

See [E 28](#) for required contraceptive measures.

Informed Consent

I 10. Capable of giving signed informed consent as described in Appendix 1 ([Section 10.1.2](#)) which includes compliance with the requirements and restrictions listed in the informed consent form (ICF) and in this protocol.

5.2 EXCLUSION CRITERIA

Participants are excluded from the study if any of the following criteria apply:

Active comparator and/or mandatory background therapy

- E 01. Clinically significant abnormal electrocardiogram (ECG) at Visit 1 that may affect the conduct of the study in the judgment of the Investigator.
- E 02. Concomitant severe diseases or diseases for which the use of ICS (eg, active pulmonary tuberculosis [[E 07](#)]) or LABA are contraindicated (eg, diagnosis of a history of significant cardiovascular diseases, insulin-dependent diabetes mellitus, hyperthyroidism, thyrotoxicosis, pheochromocytoma, hypokalemia).
- E 03. Use of injectable glucocorticosteroids or oral systemic glucocorticosteroids within 1 month prior to Visit 1/Screening or more than 4 courses of IV glucocorticosteroids within the 6 months prior to Visit 1.
- E 04. Participants receiving medications or therapy that are prohibited as concomitant medications (see [Section 6.5](#)).
- E 05. A participant with a history of clinically significant renal, hepatic, cardiovascular, metabolic, neurologic, hematologic, ophthalmologic, respiratory, gastrointestinal, cerebrovascular or other significant medical illness or disorder which, in the judgment of the Investigator, could interfere with the study or require treatment that might interfere with the study. A specific example includes but is not limited to poorly controlled insulin-dependent diabetes.
- E 06. Participants with Bronchial thermoplasty procedure (up to 3 years prior to Visit 1).

E 07. Exclusion related to tuberculosis (TB):

- Active TB or a history of incompletely treated TB.
- Confirmed Quantiferon-positive patients (no active disease) are excluded from the study unless the following conditions are met:
 - Patients with a history of prior documented completed chemoprophylaxis for latent tuberculosis infection (with a treatment regimen as per local guidelines) or treatment of active TB infection, and
 - Has obtained consultation with a specialist to rule out or treat active TB infection.
- Suspected extrapulmonary TB infection.
- Patients at high risk of contracting TB, such as close contact with individuals with active or latent TB.

Study Methodology

E 08. The exclusion criterion was deleted (Amended Protocol 01).

E 09. A current diagnosis of asthma according to the Global Initiative for Asthma (GINA) guidelines (13).

E 10. Significant pulmonary disease other than COPD (eg, lung fibrosis, sarcoidosis, interstitial lung disease, pulmonary hypertension, bronchiectasis, eosinophilic granulomatosis with polyangiitis, significant sleep apnea on Bilevel Positive Airway Pressure, etc) or another diagnosed pulmonary or systemic disease associated with elevated peripheral eosinophil counts.

E 11. Diagnosis of α -1 anti-trypsin deficiency.

E 12. Advanced COPD with need for chronic (>15 hours/day) oxygen support.

E 13. Participant with a moderate or severe AECOPD event (for definition, see [Table 1](#), primary objective) within 4 weeks prior to screening.

E 14. A participant who has experienced an upper or lower respiratory tract infection within 4 weeks prior to Screening/Visit 1 or during the screening period.

E 15. Prior history of or planned pneumonectomy or lung volume reduction surgery.

E 16. Participants with a history of a systemic hypersensitivity reaction to a mAb drug.

E 17. Anti-IgE therapy (eg, omalizumab [Xolair[®]]) within 130 days prior to Visit 1 or any other biologic therapy (including anti-IL5 mAb, e.g. benralizumab [Fasenra[®]] or mepolizumab [Nucala[®]]) for asthma or systemic immunosuppressant (e.g., methotrexate) to treat other inflammatory disease or autoimmune disease (eg, rheumatoid arthritis, inflammatory bowel disease, primary biliary cirrhosis, systemic lupus erythematosus, multiple sclerosis, etc) and other diseases, within 2 months or 5 half-lives prior to Visit 1, whichever is longer.

- E 18. Current history of substance and/or alcohol abuse.
- E 19. Inability to follow the procedures of the study (eg, due to language problems, psychological disorders) or unable to read, understand and fill a questionnaire or use an electronic diary without any help.
- E 20. Exposure to another investigative drug (small molecules as well as mAbs, including dupilumab) within a time period prior to Visit 1 that is <5 PK half-lives of the antibody. In case the half-life is not known, then the minimum interval since the exposure to the prior investigative antibody is 6 months. The minimum interval since exposure to any other (nonantibody) investigative study medication is 30 days prior to Visit 1.
- E 21. Patients who are participating in the acute phase of a pulmonary rehabilitation program, i.e. who started rehabilitation <4 weeks prior to screening (Note: patients in the maintenance phase of a rehabilitation program can be included).
- E 22. Clinically relevant (based on study Investigator's judgment) abnormal laboratory values suggesting an unknown disease and requiring further evaluation.
- E 23. Participants previously treated in any clinical trial of SAR440340.
- E 24. Participant is the Investigator, or any Subinvestigator, research assistant, pharmacist, study coordinator, other staff or relative thereof directly involved in the conduct of the study.
- E 25. Prisoners and participants who are legally institutionalized.

Current knowledge of Sanofi compounds

- E 26. Known allergy to doxycycline or related compounds, or known allergy to SAR440340 excipients.
- E 27. Females who are lactating, breastfeeding or who are pregnant.
- E 28. For Women in the study

Women of childbearing potential (premenopausal female biologically capable of becoming pregnant) who

Do not have:

- A confirmed negative serum β -human chorionic gonadotropin (β -hCG) test at Visit 1.
- Negative urine pregnancy test prior to Visit 2/Randomization.

Who are not protected by one of the acceptable forms of effective contraception (Appendix 4: Contraceptive guidance and collection of pregnancy information, see [Section 10.4](#)) (during the protocol-defined time frame from the signing of the ICF until the end of study visit).

Postmenopausal women (defined as at least 12 consecutive months without menses) are not required to use additional contraception.

For men in the study:

Male participants with female partners of childbearing potential are not eligible to participate unless they agree to ONE of the following (during the protocol-defined time frame [Appendix 4, [Section 10.4](#)])

- Are abstinent from penile-vaginal intercourse as their usual and preferred lifestyle (abstinent on a long term and persistent basis) and agree to remain abstinent.
- Agree to use a male condom plus partner use of a contraceptive method with a failure rate of <1% per year (Appendix 4, see [Section 10.4](#)) when having penile-vaginal intercourse with a woman of childbearing potential who is not currently pregnant.

Men with a pregnant or breastfeeding partner must agree to remain abstinent from penile-vaginal intercourse or use a male condom during each episode of penile penetration (during the protocol-defined time frame from the signing of the ICF until the end of study visit).

- E 29. Diagnosed active parasitic infection (helminthes), suspected or high risk of parasitic infection, unless clinical and (if necessary) laboratory assessments have ruled out active infection before randomization.
- E 30. History of human immunodeficiency virus (HIV) infection or positive HIV 1/2 serology.
- E 31. Known or suspected history of immunosuppression, including history of invasive opportunistic infections (eg, TB, histoplasmosis, listeriosis, coccidioidomycosis, pneumocystosis, aspergillosis), despite infection resolution; or unusually frequent, recurrent or prolonged infections, per Investigator's judgment.
- E 32. Live, attenuated vaccinations within 12 weeks prior to Visit 1 or planned live, attenuated vaccinations during the study (see Appendix 7: List of prohibited live, attenuated vaccines, [Section 10.7](#)).
- E 33. Patients with autoimmune disease or patients using systemic immunosuppressive therapy for autoimmune disease (eg, rheumatoid arthritis, inflammatory bowel disease, primary biliary cirrhosis, systemic lupus erythematosus, multiple sclerosis, etc) or patients with high titer autoantibodies at screening who are suspected of having high risk for developing autoimmune disease at the discretion of the Investigator or the Sponsor.
- E 34. Patients with cardiovascular diseases/conditions:
- Unstable ischemic heart disease, including acute myocardial infarction within past 1 year or unstable angina in the last 6 months.

- Cardiac arrhythmias including paroxysmal (eg, intermittent) atrial fibrillation are excluded. Patients with persistent atrial fibrillation as defined by continuous atrial fibrillation for at least 6 months and controlled with a rate control strategy (ie, selective β blocker, calcium channel blocker, pacemaker placement, digoxin or ablation therapy) and stable appropriate level of anticoagulation for at least 6 months may be considered for inclusion.
 - Cardiomyopathy, as defined by stage III-IV (New York Heart Association) cardiac failure, or other relevant cardiovascular disorder that in Investigator's judgment may put the patient at risk or negatively affect the study outcome
 - Uncontrolled hypertension (i.e. systolic blood pressure [BP] >180 mm Hg or diastolic BP >110 mm Hg despite use of anti-hypertensive therapy).
- E 35. Hepatitis B and/or C serologies indicative of active or chronic infection.
- E 36. Any prior history of malignancy or active malignancy, including lymphoproliferative diseases (except successfully-treated carcinoma in-situ of the cervix, nonmetastatic squamous cell or basal cell carcinoma of the skin) within 5 years prior to Visit 2.
- E 37. Clinically significant laboratory tests at Screening/Visit 1:
- Alanine transaminase (ALT) or aspartate transaminase (AST) >3 times upper limit of normal range (ULN).
 - Hemoglobin <10 g/dL for male and <9 g/dL for female.
 - Neutrophils <1.5 K/mm³ (<1 K/mm³ for those of African descent).
 - Platelets <100 K/mm³.
 - Creatinine \geq 150 μ mol/L.
- E 38. Patients on macrolide (eg, azithromycin) therapy, unless on stable therapy for >1 year.
- E 39. Patients on PDE-4 inhibitors (roflumilast) or leukotriene blockers (montelukast; Singulair etc).
- E 40. Despite screening of the patient, enrollment/randomization is stopped at the study level.

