5.4 SCREEN FAILURES

Screen failures are defined as participants who consent to participate in the clinical study but are not subsequently randomly assigned to IMP. A minimal set of screen failure information is required to ensure transparent reporting of screen failure participants to meet the Consolidated Standards of Reporting Trials (CONSORT) publishing requirements and to respond to queries from regulatory authorities. Minimal information includes demography, reason for screen failure, eligibility criteria, and any serious adverse event (SAE).

Patients can be rescreened if they do not meet an exclusion criterion. Patients may be rescreened one time if they do not meet the eligibility criteria (I 02) at the Screening Visit (Visit 1) or Randomization Visit (Visit 2) due to a spirometry equipment malfunction, or because the patient is unable to provide sufficient reproducible efforts. Up to 3 total attempts during the screening visit (V1) are allowed for the reasons mentioned above.

Patients who meet eligibility criteria (either meet an exclusion criterion, or who do not meet ([I 02])) may be rescreened only once during the open screening period of the study; a different patient identification number will be issued. Rescreening is not permitted if the patient fails to meet inclusion criteria, except for I 02 (see Section 6.3.1). There is no requirement for a waiting period between the screen-failure date and the rescreening date. The IVRS/IWRS report will flag rescreened patients. Patients that are rescreened must sign a new consent form and all Visit 1 procedures must be repeated.

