6.5 CONCOMITANT THERAPY

Any medication or vaccine (including over-the-counter or prescription medicines, vitamins, and/or herbal supplements) that the participant is receiving at the time of enrollment or receives during the study must be recorded along with:

- Reason for use
- Dates of administration including start and end dates
- Dosage information including dose and frequency

The following concomitant treatments are not permitted during the screening or treatment phases:

- Systemic steroids (except when used to treat exacerbations)
Note: one short-term course of systemic corticosteroids (up to 6 days) is permitted in 24 weeks, when medically necessary for reasons not related to AECOPD, eg. in the case of severe poison ivy exposure.
- PDE-4 inhibitor such as roflumilast
- Methylxanthines (theophylline, aminophyllines)
- Leukotriene receptor antagonists or leukotriene synthesis inhibitors
- Lipoxygenase inhibitors
- Anti-IL5 mAb (eg, benralizumab; mepolizumab)
- Anti-IgE therapy (eg, omalizumab)
- Anti-IL4R mAb (eg, dupilumab)
- Systemic immunosuppressants (eg, methotrexate, any anti-TNF mAbs, B and/or T cell targeted immunosuppressive therapies)
- Bronchial thermoplasty
- Intravenous immunoglobulin (IVIg) therapy
- Live Attenuated Vaccines: refer to Appendix 7: List of Prohibited Live Attenuated Vaccines, [Section 10.7](#).
- β -adrenergic receptor blockers (except for a selective β -1 adrenergic receptor blocker used with dose stable 1 month prior to Visit 1)
- COPD relievers other than salbutamol/albuterol, levosalbutamol/levalbuterol or ipratropium: their use is not recommended during the study period. In case of use in exceptional circumstances (eg, prescribed by a physician not participating in the study), their use will be documented in the patient's file and reported in the eCRF.
- Other investigational drugs

Note: The following is a list of permitted concomitant medications during the study:

- Antihistamines are permitted as concomitant medication
- Ocular, intranasal, and topical corticosteroids are permitted during the study.

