8.1 EFFICACY ASSESSMENTS

8.1.1 Disease-specific efficacy measures

8.1.1.1 COPD exacerbation

Severity of COPD exacerbations as defined by the protocol

“Moderate exacerbations” are recorded by the Investigator and defined as AECOPD that require either systemic corticosteroids (such as intramuscular, intravenous or oral) and/or antibiotics. “Severe exacerbations” are recorded by the Investigator and defined as AECOPD requiring hospitalization, emergency medical care visit or resulting in death.

All other exacerbations will be classified as “mild”.

Clinical symptoms of exacerbations of COPD

In addition to the protocol-defined exacerbations of COPD listed above, clinical signs and symptoms of exacerbations of COPD will be captured in the eCRF (including, but not limited to increase in dyspnea, increase in wheezing, increase in cough, increase in sputum volume and/or increase in sputum purulence).

Management of exacerbations of COPD

Exacerbations of COPD should be treated as deemed necessary by the investigator. After successful management of an acute exacerbation of COPD (e.g. with oral corticosteroids and/or antibiotics), all efforts should be made to resume the initial background COPD treatment regimen if in the investigator's opinion this is medically acceptable. After 1 severe or 2 moderate exacerbations of COPD, dose adjustments in background therapy will be permitted for symptom control and as needed for the remainder of the trial period.

Protocol defined COPD exacerbation events are collected as efficacy endpoints via the exacerbation eCRF page. These events should not be reported as AEs unless they fulfill a seriousness criterion. Any course of systemic steroids/antibiotics started <7 days of finishing a previous course should be considered as treatment for a single exacerbation.

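### E13 and E03 stop at Visit 1 while E14 runs through screening, so an exacerbation or steroid course before Day 1 can enter the FEV1 and eosinophil baselines

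*Protocol*

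**What the plan says.** Three exclusions in Protocol section 5.2 have different end points:

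- E13: "Participant with a moderate or severe AECOPD event (for definition, see [Table 1](#), primary objective) within 4 weeks prior to screening".
- E03: "Use of injectable glucocorticosteroids or oral systemic glucocorticosteroids within 1 month prior to Visit 1/Screening".
- E14: "A participant who has experienced an upper or lower respiratory tract infection within 4 weeks prior to Screening/Visit 1 or during the screening period".

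Section 4.1 gives a screening period of 10 days to 4 weeks between Visit 1 and randomization at Visit 2 (Day 1).

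E04 excludes "Participants receiving medications or therapy that are prohibited as concomitant medications" and refers to section 6.5. The list there opens with "The following concomitant treatments are not permitted during the screening or treatment phases", and its first entry is "Systemic steroids (except when used to treat exacerbations". A note under that entry also permits one course of up to 6 days per 24 weeks for a reason other than AECOPD.

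SAP section 2.1.1 defines baseline as the last value before the first dose. SAP section 2.4.4.2.1 uses baseline FEV1 both to form the change score and as a covariate. SAP section 2.4.4 builds the eosinophil strata from the actual baseline count, not the screening count used to stratify randomization. SAP section 2.3.1 defines the high-eosinophil population from that same baseline count.

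For counting events, Protocol section 8.1.1.1 states: "Any course of systemic steroids/antibiotics started <7 days of finishing a previous course should be considered as treatment for a single exacerbation".

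For rescreening, the text in Protocol sections 5.4 and 6.3.1 starts with "Patients can be rescreened if they do not meet an exclusion criterion". A later paragraph in each section allows one rescreening for patients who do meet an exclusion criterion. Section 5.4 adds that no interval is required before rescreening.

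**The concern.** The evident purpose of E13 and E03 is that patients enter in a stable state. Their windows leave uncovered the days closest to baseline. A patient can have a moderate AECOPD in the second week of screening, take oral steroids up to Day 1, and still be eligible if the site does not record a respiratory infection. The eligibility checks repeated at Visit 2 do not reliably stop this. I02 requires post-bronchodilator FEV1 between 30% and 80% of predicted, and I03 requires a CAT score of at least 10, where a higher score means worse health.

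Two analysis inputs are exposed:

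- **Baseline FEV1.** If the Visit 2 value is measured during or just after an exacerbation, later recovery appears as change from baseline in either arm.
- **Baseline eosinophil count.** If a systemic steroid course falls between the Visit 1 and Day 1 counts, a patient may cross 250/mm³. That changes the covariate value and membership of the high-eosinophil population.

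**Working it through.** **1. Does any criterion cover Visit 1 to Visit 2?**

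| Rule | Subject | Covers screening? |
|---|---|---|
| E13 | moderate or severe AECOPD | no |
| E03 | systemic steroids | no |
| E14 | respiratory infection | yes |
| E04 with 6.5 | prohibited medication | yes, but exacerbation steroids and one short other course are exempt |
| E05 | significant illness | investigator's judgment only |

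The uncovered cases are a screening exacerbation not labelled an infection, and a steroid course allowed by section 6.5.

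**2. Check of the plan's inputs.** Protocol section 9.2 gives a placebo rate of 1.0 to 1.5 per year, dispersion k = 1.5, 170 patients per arm, a two-sided 5% Wald test, and the accrual and dropout pattern. Follow-up times t were simulated from that pattern, with a mean of 35.5 weeks (SD 12.8), as stated. Information per arm is I = 170 × E[λt/(1 + 1.5λt)], and power is Φ(|ln 0.55|/√(1/I₀ + 1/I₁) − 1.96). At rates 1.0, 1.2 and 1.5 this gives 81.6%, 85.2% and 88.8%, which are the plan's own figures for a 45% reduction. The rate and dispersion are therefore read as the plan uses them.

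**3. Chance of at least one event in screening.** This assumes that the on-study placebo rate also applies in screening. P = 1 − (1 + kμ)^(−1/k), with μ = rate × days/365.25.

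| Rate per year | Days | μ | P | Of 340 |
|---|---|---|---|---|
| 1.0 | 10 | 0.0274 | 2.65% | 9.0 |
| 1.0 | 28 | 0.0767 | 7.0% | 23.8 |
| 1.5 | 10 | 0.0411 | 3.9% | 13.3 |
| 1.5 | 28 | 0.1150 | 10.1% | 34.2 |

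**4. Allowance for E13 itself.** E13 selects patients who were event-free for the previous 28 days. Under the same model, P = 1 − [(1 + k(μ₂₈ + μ))/(1 + kμ₂₈)]^(−1/k).

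- Lowest case (1.0 per year, 10 days): 1 − (1.1561/1.1150)^(−1/1.5) = 2.4%, about 8 of 340.
- Highest case (1.5 per year, 28 days): 1 − (1.3450/1.1725)^(−1/1.5) = 8.7%, about 30 of 340.

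**5. Allowance for E14.** The documents do not give the share of exacerbations that would not be coded as infections. At an assumed 20% to 50%, the step 3 figures give 0.2 × 9.0 = 1.8 to 0.5 × 34.2 = 17.1, or about 2 to 17 patients. The step 4 figures give about 2 to 15.

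**6. If carried-over events were counted (illustration only).** Take constant exposure of 35.5/52.18 = 0.680 years and a true rate ratio of 0.55, and add 5 events to each arm.

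- Rate 1.0: (63.6 + 5)/(115.7 + 5) = 0.57. Power in this simplified model goes from 83.1% to 80.1%.
- Rate 1.5: (95.4 + 5)/(173.5 + 5) = 0.56. Power goes from 90.1% to 88.4%.

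**The case against.** The strongest reply is that E14 already does most of the work. Protocol section 2.2.1 says exacerbations are most often due to viral and bacterial lung infections, and E14 excludes those in screening. E05 adds investigator discretion. This stands as a reason why the number affected is small. It does not close the gap, because E14 depends on how the site labels the episode, whereas section 8.1.1.1 defines a moderate exacerbation by the treatment it requires.

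On eosinophils, SAP section 2.4.4.1 prespecifies a subgroup analysis by randomization stratum, which uses the Visit 1 count, and SAP section 2.4.4.2.1 repeats it for FEV1. That is a partial safeguard. The covariate and the high-eosinophil population still use the later count.

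A reader might infer two stronger points that the documents do not support:

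- **That the screening episode goes unrecorded.** Investigator exacerbation reporting starts at Visit 2, but the Schedule of Activities (footnote b) makes Visit 2 assessments pre-dose. The diary logs exacerbation steroids and antibiotics daily during screening (section 8.1.2), and all medication is recorded with reason and dates (section 6.5).
- **That the first on-study event is contaminated.** The primary analysis counts events from randomization (SAP section 2.4.4.1), and time to first event uses the onset date (SAP section 2.4.4.2.3). The 7-day rule would assign a continuing course to the earlier episode. Contamination is possible but not established. What remains is that the SAP does not repeat that rule and does not address an episode spanning randomization.

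**Conclusion.** The gap is real and small. As written, the plan allows randomization during or just after a screening exacerbation that is not labelled an infection, or after a permitted steroid course. The firm consequence concerns baseline: added noise in change from baseline in FEV1, and possible misclassification in the eosinophil covariate and the high-eosinophil population.

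The estimate is 9 to 34 of 340 patients before E14 and about 2 to 17 after it. It assumes that the on-study rate applies in screening and that 20% to 50% of events escape E14. The top figure also needs the highest rate and 28 days of screening for everyone. Steroid courses for reasons other than AECOPD are not in the estimate. The documents give no basis for sizing the effect on FEV1 variance.

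A reader might also infer bias in favour of one arm. Blinded 1:1 randomization makes the expected effect noise and dilution in both arms. The change is worth making because it is cheap.

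**What to change.** 1. **Protocol section 5.2.** Extend E13 and E03 with the closing words of E14, so that all three windows cover screening. Final eligibility wording is for the sponsor.
2. **Protocol section 6.5.** Reconcile the two steroid exceptions, as they apply to the screening phase, with the revised E03. Otherwise a course allowed by 6.5 would be an exclusion under 5.2. The point concerns whether such a patient goes on to randomization, not how an exacerbation is treated.
3. **Protocol sections 5.4 and 6.3.1.** Correct the first rescreening sentence, which contradicts the later paragraph. No separate waiting rule is needed, because E13 and E03 apply again at the new Visit 1. The sentence in 5.4 saying that no interval is required should state this.
4. **SAP sections 2.4.4.1 and 2.4.4.2.3.** State that an exacerbation with onset before randomization, including later courses merged with it under the 7-day rule, is not counted as an on-study event.

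The cost is two phrases in 5.2, reconciling text in 6.5, two corrected sentences on rescreening (one of them in both sections) and one sentence in the SAP. Sample size and power are unchanged. The downside is a few more screen failures, most of whom could return through the single rescreening.
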